## 8. STATISTICAL METHODS

### 8.1. STATISTICAL SOFTWARE AND METHODOLOGY

The statistical analysis will be performed by Institut de Recherche Pierre Fabre. Data will be analysed using the SAS® system software version 9.4 (or later if available) for Windows®. All statistical tests will be two-sided at a 5% level of significance unless otherwise specified.

Summary tables will be provided according to the standard format of Institut de Recherche Pierre Fabre developed for the vinflunine chemotherapy.

All descriptive statistics will be presented in summary tables by treatment arm.

Continuous data will be summarized with the following items: frequency, median (if  $n > 3$ ), range and mean and standard deviation if relevant.

Categorical data will be presented in contingency tables with frequencies and percentages of each modality (including missing data modality).

### 8.2. STATISTICAL METHODS FOR CATEGORICAL VARIABLES

The  $\chi^2$  test will be performed to compare proportions or replaced by Fisher's exact test if the expected frequency in one cell of the contingency table is less than 5. The 95% confidence interval for proportions will be computed following the exact method. If a stratified analysis is required a Cochran-Mantel-Haenszel (CMH) test will be used.

### 8.3. STATISTICAL METHODS FOR ORDINAL VARIABLES

Comparisons between the two treatment arms will be provided for ordinal data using the non-parametric Wilcoxon rank sum test.

### 8.4. STATISTICAL METHODS FOR CONTINUOUS VARIABLES

The distributions of quantitative data will be examined by the Kolmogorov-Smirnov test in order to test for normality. In case of Gaussian distribution, the comparison between the 2 treatment arms will be made with a Student t-test. If the distribution is not considered as Gaussian then the non-parametric Wilcoxon test will be performed.

## 8.5. STATISTICAL METHODS FOR TIME DEPENDENT DATA

To describe time dependent parameters, Kaplan-Meier curves and life tables by treatment arm will be provided. Confidence intervals on the median will be calculated using the Brookmeyer and Crowley method. Hazard ratio and 95% confidence intervals will be reported. A stratified Cox proportional model will be performed to compare the two treatment arms taking into account the stratification factors (except center) used at the time of randomisation.

According to the protocol amendment 11, no multivariate analysis will be performed.

## 8.6. STATISTICAL METHODS FOR HEALTH-RELATED QUALITY OF LIFE DATA

Following the protocol amendment 11, no repeated measure analysis will be performed.

# 9. TREATMENT GROUP DESCRIPTION

## 9.1. DESCRIPTION AT BASELINE

Analysis of baseline characteristics and demography will be performed on the ITT population, by treatment arm.

### 9.1.1. Overview of the study

The reasons for treatment discontinuation will be reported. Study discontinuation will be described according to the following reasons: adverse event (related or not), death, progressive disease, lost to follow up, protocol deviation and other reasons.

The patient status (dead or alive) at the cut-off date will be displayed together with each reason of death (progressive disease, related adverse event, other).

The number of patients randomised, treated (evaluable for safety) and evaluable for quality of life will be presented by treatment group. Patients with at least one protocol deviations will be tabulated by treatment arm and by type of protocol deviation.

For arm A, the treatment duration is defined as the time elapsed between the date of 1st administration and the date of the last VFL administration (if MTX not given) + 21 days or the date of the last MTX administration (if given) + 14 days. For arm B, the treatment duration is defined as the time elapsed between the date of the 1st administration and the date of the last D1 administration of the last cycle + 21 days (if D8 and D15 not given) or the date of the last D8 administration of the last cycle + 14 days (if D15 not given) or the date of the last D15 administration of the last cycle + 7 days (if D15 given). Treatment duration will be tabulated by treatment arm.

Time between randomisation and first administration will be tabulated by treatment arm.

The duration of follow-up is defined as the time elapsed between the date of randomisation and the date of last news or death, death being a censored observation.

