5.1.1.3. Methotrexate

Mouthwash is recommended as prophylaxis of stomatitis.

On day 1, methotrexate will be administered by direct bolus injection through the side arm of the remaining NS or 5% glucose solution bag after completion of vinflunine infusion.

On day 8, methotrexate will be administered through the side arm of a freely running NS or 5% glucose solution IV infusion.

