## 9.2. DESCRIPTION DURING THE STUDY

**Description during the study will be done on all treated population.**

A summary table will provide by treatment arm (and by treatment), the following items:

- Duration of exposure,
- Number of patient with at least one dose permanently discontinued,
- Number of patient with at least one dose cancelled,
- Number of patients with at least one dose reduced,
- Number of patients with at least one dose delayed,
- Number of patients with at least one infusion interrupted.

The total number of cycles given during the study, the median number of cycles as well as the number of patients by cycle will be given. The number of methotrexate administration will be presented in each arm.

The actual dose of (mg/m^2) will be calculated from the total dose administered (mg) divided by the BSA.

The BSA will be recalculated at each cycle.

The Body Surface Area (BSA) will be calculated as follows :

$$\text{BSA} = \frac{(W^{0.425} \cdot H^{0.725} \cdot 71.84)}{10000}$$

where :

- W = Weight (in kg) at cycle before cycle *i*, or last weight available if missing,
- H = Height (in centimetres) at the beginning of the study.

BSA as per investigator will be used as an estimate when height is not provided at baseline.

The following categories of vinflunine doses will be used:

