### 9.2.1. Dose intensity per cycle

Actual dose intensity per cycle will be defined as follows :

$$DI \text{ at cycle } i = \frac{\text{Actual dose received at cycle } i}{\text{Actual duration of cycle } i \text{ (wk)}} = \frac{\text{Actual dose received at cycle } i}{[(\text{Course date at cycle } i + 1) - (\text{Course date at cycle } i)]}$$

The cycle duration at cycle n will be equal to the time elapsed between the day 1 administration date of cycle n and the day 1 administration date of cycle n+1. The duration of the last cycle will be estimated to be 3 weeks.

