### 9.2.3. Dose intensity per patient

Actual dose intensity per patient will be defined as follows:

$$DI = \frac{\text{Cumulative dose}}{\text{Treatment duration (wk)}} = \frac{\sum_{i=1}^n \text{dose}_i}{\sum_{i=1}^n \text{duration}_i}$$

where:

- dosei = actual dose received (mg/m^2) at cycle *i*,
- durationi = actual duration (wks) of cycle *i*,
- n = total number of cycle(s) per patient.

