### 9.2.6. **Treatment cancellation**

Cancellation of day 1 vinflunine administration is not allowed by the protocol. Methotrexate dosing may be cancelled in both arms (D8 in Arm A and D8/D15 in Arm B) as per protocol (§ 5.2.3 and § 5.2.4 of the protocol).

The number of cycles with at least one day of methotrexate cancelled and number of patients with at least one day of dosing cancelled will be displayed. Reasons for treatment cancellation will be provided.

Number of patients with at least one methotrexate dose cancelled,

Number of cycles with at least one methotrexate dose cancelled,

- Reasons for methotrexate on D1 / D8 / D15 dose cancellation, per patient and per cycle,
- Listing of methotrexate dose cancelled and reason,

If cancellation are observed for Vinflunine, they will be described in the same way as for Methotrexate.

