### **9.2.8. Treatment delay**

The number of patients and cycles delayed will be presented with reasons for treatment delay.

A treatment cycle will be considered as delayed if administered  $\geq 4$  days after the planned date with a three weeks interval from day 1 of previous cycle.

The delays will be categorized as follows:

- [4 – 7 days],
- [7 – 14 days],
- 14 days.

The following information will be described:

- Number of patients with at least one cycle delayed by four days or more, by arm
- Number of cycles delayed, by arm
- Categorized groups of cycle delay, by arm
- Reasons for cycle delay of four days or more, by arm
- Listing of the cycles delayed with reasons,

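### The arm A treatment-duration rule counts 28 days instead of 21 for a last cycle whose day 8 methotrexate dose moved to day 15, and is ambiguous when that dose was cancelled

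*SAP*

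**What the plan says.** SAP 9.1.1 defines treatment duration from the first administration to an end date that differs by arm; SAP 15.2.4.4 repeats the definition.

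- **Arm A.** The end is the last vinflunine date + 21 days when methotrexate was not given, and otherwise "the date of the last MTX administration (if given) + 14 days". No study day is attached to the methotrexate branch.
- **Arm B.** Each offset is tied to a day of the last cycle: day 1 + 21, day 8 + 14, and "the date of the last D15 administration of the last cycle + 7 days (if D15 given").

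Other sections bear on the same interval:

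- Protocol 5.1.1.3: in arm A, day 1 methotrexate goes through the "glucose solution bag after completion of vinflunine infusion", so both drugs share the day 1 date.
- Protocol 5.2.3.2 and Table 10: low counts move the arm A day 8 dose by one week to day 15, and it is cancelled if there is no recovery. Protocol 5.2.3.3 cancels it for certain non-haematological toxicities.
- SAP 9.2.6: "Methotrexate dosing may be cancelled in both arms (D8 in Arm A and D8/D15 in Arm B) as per protocol".
- SAP 9.2.1: "The duration of the last cycle will be estimated to be 3 weeks".
- SAP 9.2.8: a cycle is late by reference to "days after the planned date with a three weeks interval from day 1 of previous cycle".
- SAP 9.2.3: the denominator of dose intensity per patient is labelled "Treatment duration (wk") and is the sum of the cycle durations.
- SAP 9.2 also lists "Duration of exposure" without defining it.

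**The concern.** The arm B offsets shrink as the last dose falls later in the cycle, so each one completes 21 days. The arm A methotrexate offset stays at 14 even though the protocol itself allows that dose on day 15. The one-week move exists only in arm A: protocol 5.2.4.2 (Table 15) and 5.2.4.3 cancel arm B day 8 and day 15 doses rather than moving them. A planned schedule change therefore lengthens the tabulated duration in one arm only.

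Treatment duration is tabulated by arm and listed by patient. At stake are a like-for-like description of exposure and having one value for one term: SAP 9.1.1 and 9.2.3 would give different treatment durations for the same arm A patient.

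**Working it through.** **Inputs.** Offsets: SAP 9.1.1. Cycle length of 3 weeks = 21 days: SAP 9.2.1 and 9.2.2. Permitted day 8 changes: protocol 5.2.3.2, Table 10 and 5.2.3.3. Conversion to months: SAP 15.2.1.1, (days + 1) / 30.4375.

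**Formula.** Days credited to the last cycle = (study day of the reference dose − 1) + offset.

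**Reproducing the plan's 21 days.** Arm A with day 8 on time: 7 + 14 = 21. Arm B: 0 + 21 = 21, 7 + 14 = 21, 14 + 7 = 21. The rule works on schedule in both arms.

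**The permitted departures in arm A, read at last-cycle level:**

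| Last cycle, arm A | Condition refers to any methotrexate | Condition refers to the day 8 dose |
|---|---|---|
| Day 8 on time | 7 + 14 = 21 | 7 + 14 = 21 |
| Day 8 moved to day 15 | 14 + 14 = 28 | 14 + 14 = 28 |
| Day 1 given, day 8 cancelled | 0 + 14 = 14 | 0 + 21 = 21 |
| Vinflunine only | 0 + 21 = 21 | 0 + 21 = 21 |

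The moved dose gives 28 days in both columns. The cancelled dose depends on the reading.

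**Relative size of 7 days.** One cycle: 7/21 = 33.3%. Two cycles: 7/42 = 16.7%. Four cycles: 7/84 = 8.3%.

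**In months, two cycles.**
- Correct: (42 + 1)/30.4375 = 1.41.
- Last day 8 moved: (49 + 1)/30.4375 = 1.64.
- Last day 8 cancelled, first reading: (35 + 1)/30.4375 = 1.18.

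In weeks, the moved case is 49/7 = 7 under SAP 9.1.1 and 42/7 = 6 under SAP 9.2.3.

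**Is 28 days a legitimate cycle length?** A new cycle starting 14 days after a day 15 dose begins on day 29, which is 28 days after day 1. That is 28 − 21 = 7 days late under SAP 9.2.8, whose limit is 4.

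**Shift in the arm A mean.** Shift = 7 × (share moved − share cancelled), counting only changes in the last cycle. The documents give neither share. Assuming 0 to 30% for each:
- Condition refers to any methotrexate: −7 × 0.30 = −2.1 to 7 × 0.30 = +2.1 days.
- Condition refers to the day 8 dose: 0 to +2.1 days.

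Each 10% is worth 7 × 0.10 = 0.7 days and at most 0.10 × 230 = 23 patients. The 230 are those randomised to arm A; only treated patients have a duration.

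**The case against.** **The cancelled-dose case may not be an error.** A reader might infer that the rule definitely gives 14 days whenever day 8 is cancelled. The documents do not support that as a certainty. The arm B conditions each turn on whether a later dose of the cycle was given. Read in parallel, the arm A condition would concern the day 8 dose, and a cancelled day 8 would get vinflunine + 21 = 21 days. The literal reading also has an odd result: the same day 1 date earns 21 days if methotrexate was omitted and 14 if it was given. That counts against its being intended. On the other side, the arm B clause names its days and the arm A clause does not. This objection stands to the extent that the case is an ambiguity to settle.

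**The protocol does use a 14-day interval.** Protocol 5.2.2.2 and 5.2.3.2 also call a cycle delayed at 14 + 4 days or more after the last day 8 dose, so the + 14 may come from there. This does not rescue the 28 days. The alternative limb of the same rule counts a cycle as delayed at 21 + 4 = 25 days or more after day 1, and day 29 is 28 days after it.

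**The effect is small.** It arises only when the change falls in a patient's last cycle. SAP 8.1 reports the median and range, with the mean only if relevant, and no test of treatment duration is specified. All of this is right and supports a minor rating.

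**A reader might infer that dose intensity is distorted**, because SAP 9.2.3 uses the same label. It is not: 9.2.3 gives its own formula, the sum of cycle durations, with the last cycle fixed at three weeks by 9.2.1.

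**Conclusion.** The rule is wrong as written for a moved day 8 dose: 28 days instead of 21 in the last cycle under either reading of the condition, or +7 days per affected patient. For a cancelled day 8 after day 1 methotrexate the wording is ambiguous: −7 days if the condition covers any methotrexate, no error if it covers the day 8 dose.

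Both results assume that the arm A rule works at last-cycle level, as arm B does. A reader might instead take the last methotrexate date over the whole treatment. A patient who stopped methotrexate after day 8 of cycle 1 and stayed on vinflunine alone through cycle 4, as protocol 5.2.5 permits, would then count 7 + 14 = 21 days instead of 63 + 21 = 84. The parallel arm B wording makes that reading unlikely, so it is not part of the finding, but a revised text should exclude it.

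The shares affected are unknown, and the mean shifts above rest on assumed shares. The effect is confined to descriptive treatment duration, plus duration of exposure if the SAP means the same variable. Overall survival runs from randomisation, dose intensity and relative dose intensity have their own denominator, and the adverse-event window in SAP 5.1 ends 30 days after the last administration; none of these uses the rule. Severity: minor.

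**What to change.** In SAP 9.1.1 and 15.2.4.4, define treatment duration in **both** arms as the date of day 1 of the last cycle in which any study drug was given + 21 days, minus the date of first administration. This equals the sum of cycle durations in 9.2.3 with the three-week last cycle of 9.2.1. It settles the cancelled-dose ambiguity and rules out the whole-treatment reading. Changing arm A alone would leave the arms on different anchors, because a late arm B dose in the last cycle would still add its days.

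An alternative that gives the same result for on-schedule doses is to give arm A the arm B offsets at last-cycle level, counting either drug: last dose on day 1 + 21, on day 8 + 14, on day 15 + 7.

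State in SAP 9.2 whether duration of exposure is this variable.

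The cost is one replaced definition in two sections, one added sentence, and a simpler derivation. With the day 1 anchor, a late dose within the last cycle no longer extends the duration in either arm.

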### 9.1.2. Characteristics at baseline

Demographic and baseline characteristics of patients will be displayed. The following variables will be analysed on the ITT population according to the arm assigned at randomisation:

#### Demographic data

- Age at the time of randomisation
- Categorized groups of age : < 35, [35 – 50[, [50 – 65[, [65 – 75[, [75 – 80[ and  $\geq$  80 years
- Sex
- Body weight,
- WHO Performance Status

#### Stratification data Extract from the IWRS database

- WHO performance status (0 vs. 1),
- Refractory or resistant to platinum versus other
- Prior radiotherapy (yes versus no)
- Prior treatment with any anti-EGFR medication (yes versus no)

#### Tumour characteristics at diagnosis

- Anatomic site of cancer,
- Histopathological grade,
- TNM classification,
- Stage,

#### Tumour characteristics at study entry

- Extent of the disease at study entry,
- Patient category,
- Interval from diagnosis to study entry (randomisation),
- Categorized groups of Interval from diagnosis to study entry (< 2 years vs.  $\geq$  2 years),
- Progression-free interval\***,
- Categorized groups of progression-free interval (< 6 months vs.  $\geq$  6 months),
- Treatment free interval\*\***,
- Categorized groups of treatment free interval (< 6 months vs.  $\geq$  6 months),
- Disease free interval\*\*\***
- Categorized groups of disease free interval\*\* : <2 years,  $\geq$  2 years,
- Presence of visceral involvement (lung +/- liver),
- Presence of visceral involvement (such as liver, lung, pleura, heart, pericardium, kidney, thyroid and suprarenal gland, detailed list in appendix 4)
- Categorized groups of number of organs involved: 1, 2 and • 3 organs,

- Detail of organs involved, grouping provided in appendix 4
- Measurable/non-measurable disease\*\*\*\*.

\* : The **progression free interval** is the time interval elapsed between the date of end of the last prior chemotherapy given for metastatic intent and the date of relapse or progression after this last line of chemotherapy. This progression free interval of patients relapsing or progressing during the last line treatment will be estimated to last one day.

\*\* : The **treatment free interval** is the time elapsed between the date of end of the last treatment (prior chemotherapy, prior radiotherapy, prior treatment with cetuximab, whichever occurs last) and the first administration of study treatment.

\*\*\*The **disease free interval** is the time interval elapsed between the date of end of the last prior chemotherapy according to intents induction/concomitant with radiotherapy and the date of relapse or progression.

\*\*\*\* **Measurable disease** defined as:

- Yes if the number of targeted lesions is > 0,
- No if number of targeted lesions is not > 0 and the number of non-targeted lesions is > 0
- No disease in other cases

### Prior therapy

An overview of prior therapies for SCCHN will be provided giving:

- Number of patients with at least one prior therapy
- Number of patients treated by medication
  - Number of patients treated by chemotherapy
  - Number of patients treated by cetuximab
  - Number of patients treated by other antineoplastic drug
- Number of patients who underwent a surgery, excluding biopsies,
- Number of patients who underwent a radiotherapy
- For the last Medication (including chemotherapy, cetuximab, antineoplastic therapy): intent, time between stop date of medication and date of relapse/progression (expressed in weeks).
- For surgeries: number of surgeries
- For the last radiotherapy: intent
- Number of patients by combination of therapies:
  - Chemotherapy + radiotherapy + surgery
  - Chemotherapy + radiotherapy
  - Chemotherapy + surgery

### *Surgery*

- Details of surgeries using MedDRA system organ class and preferred term,

### *Radiotherapy*

- Number of patients who underwent a radiotherapy (for SCCHN) with intent and intent of last radiotherapy,

### *Chemotherapy*

Number of patients who underwent a chemotherapy (for SCCHN) with intent and intent of last chemotherapy,

Number of lines,

Number of patients treated with a prior platinum agent (Cisplatin, Carboplatin, ...),

Type of prior platinum-based chemotherapy by intent

Number of refractory/resistant/other failure patients by intent for prior platinum-based chemotherapy

Class of prior adjuvant/induction chemotherapy: (Platinum single agent, Platinum + Taxane, Platinum + Other, Taxane single agent, Taxane + Other)

Class of prior metastatic chemotherapy: (Platinum single agent, Platinum + Taxane, Platinum + Other, Taxane single agent, Taxane + Other)

Number of cycles of chemotherapy by intent and by class of chemotherapy,

Best response of the last chemotherapy by intent and by class of chemotherapy,

### Other prior treatments

Number of patients who underwent a treatment with cetuximab (including panitumumab) with intent and intent of last treatment,

Number of patients who underwent a prior treatment with other antineoplastic drugs with intent,

### Clinical examination

Electrocardiogram (normal/abnormal but not clinically significant/abnormal clinically significant),

Baseline biological abnormalities,

Baseline haematological abnormalities.

Temperature, Blood Pressure, Pulse

### Concomitant medications at baseline

Concomitant medications whatever the indication, according to the WHO-Drug dictionary,

Concomitant medications with a tumour related indication, according to the WHO-Drug dictionary,

Concomitant medications with a prophylactic indication, according to the WHO-Drug dictionary

Concomitant medications with pre-treatment event indication, according to the WHO-Drug dictionary,

Concomitant medications with a medical history indication,

### Prior medical history

Prior medical history according to MedDRA System Organ Classification (SOC) and Preferred Term (PT),

Listing of prior medical or surgical history,

### Pre-treatment events

Pre-treatment events according to MedDRA System Organ Classification (SOC) and Preferred Term (PT),

Listing of Pre-treatment events at baseline.

## 9.2. DESCRIPTION DURING THE STUDY

**Description during the study will be done on all treated population.**

A summary table will provide by treatment arm (and by treatment), the following items:

- Duration of exposure,
- Number of patient with at least one dose permanently discontinued,
- Number of patient with at least one dose cancelled,
- Number of patients with at least one dose reduced,
- Number of patients with at least one dose delayed,
- Number of patients with at least one infusion interrupted.

The total number of cycles given during the study, the median number of cycles as well as the number of patients by cycle will be given. The number of methotrexate administration will be presented in each arm.

The actual dose of (mg/m^2) will be calculated from the total dose administered (mg) divided by the BSA.

The BSA will be recalculated at each cycle.

The Body Surface Area (BSA) will be calculated as follows :

$$\text{BSA} = \frac{(W^{0.425} \cdot H^{0.725} \cdot 71.84)}{10000}$$

where :

- W = Weight (in kg) at cycle before cycle *i*, or last weight available if missing,
- H = Height (in centimetres) at the beginning of the study.

BSA as per investigator will be used as an estimate when height is not provided at baseline.

The following categories of vinflunine doses will be used:

